8.3.2. Nicotine Use

Nicotine use will be collected at Screening and listed only by subject for the Dose Selection Randomized Population.

8.4. MEDICAL HISTORY

Medical history will be listed by subject for the Dose Selection Randomized Population. Medical history will be coded into the most recent version of Medical Dictionary for Regulatory Activities (MedDRA) available (version 20.0 or later). All findings on medical history will be evaluated by the investigator for clinical significance.

The DSM-IV-TR modules will be used to screen for alcohol and substance dependence but shall not be listed.

8.5. PRIOR AND CONCOMITANT MEDICATION

Prior medication is defined as medication taken up to 30 days before the first screening date. Non-study medication taken from the first Screening visit until the completion of the Follow-up visit will be considered as concomitant. Prior and concomitant medications will be assigned a 12-digit code using the most recent version of the World Health Organization drug codes available (WHO Drug). The original verbatim terms collected in the electronic Case Report Form (eCRF) for prior and concomitant medications will be coded using the World Health Organization Drug Dictionary (WHO-DD) into drug class (Anatomical Therapeutic Chemical [ATC] Classification level 2) and preferred term (PT).

Prior and concomitant medications will be listed chronologically by subject including all data collected in the eCRF, along with coded variables for Dose Selection Randomized

Population. The incidence of concomitant antiemetic medication use will be tabulated by cohort (i.e., dose level) and treatment (active drug or placebo).

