## **4.6 Study Restrictions**

### **4.6.1 Prohibited Medications**

Subjects will be required to avoid using non-prescription medication (except nicotine-containing substances and acetaminophen up to 2000 mg per day) within 7 days prior to first drug administration and throughout the study, unless in the opinion of the medical monitor, in consultation with the investigator or designee, the product will not interfere with the study procedures or data integrity or compromise the safety of the subject.

Subjects will be required to avoid using prescription medications or natural health products (except vitamin or mineral supplements, acceptable forms of birth control, and hormone replacement) within 14 days prior to first drug administration and throughout the study, unless in the opinion of the investigator or designee, the product will not interfere with the study procedures or data integrity or compromise the safety of the subject.

Concomitant medications are prohibited in this study unless prescribed by the investigator to treat clinical events or exempted by the investigator on a case-by-case basis because they would be unlikely to affect the study results or subject safety (eg, topical medications). All medications taken by subjects after Screening until the completion of the Follow-up visit will be documented

as concomitant medications. The reported medications will be reviewed and evaluated by the investigator to determine if they affect a subject's eligibility or continued participation in the study.

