7.3. MISSING DATA

For PD and PK analyses, missing data for subjects who are administered all scheduled study treatments for all the treatment periods will be considered as random non-informative missing for analysis purposes. Missing values will be examined on a case-by-case basis to confirm this. Missing values for PD assessments will not be imputed. The handling of missing PK data is detailed in Section 10.4.

AEs and medications with incomplete start dates and times will be considered as treatment-emergent or prior/concomitant, respectively, according to the following algorithm:

1. If the AE occurrence type is specified for the AE on the eCRF, it will be used to determine treatment-emergence. If the AE occurrence type is ‘Treatment Period X’ then the AE will be assigned as treatment-emergent. This will be verified using the algorithms below (steps 3 through 7).
2. If a medication started and stopped prior to the start of study treatment the medication will be considered prior. This will be verified using the algorithms below (steps 3 through 7).
3. Comments will be reviewed for additional information when treatment emergence is ambiguous.
4. Only the start year is reported: If the year is after or the same as the year of the first dose date, then the event will be considered treatment-emergent.

5. Only the start month and year are reported: If the month/year is after or the same as the month/year of the first dose date, then the event will be considered treatment-emergent.
6. Only the start time is missing: If the event occurred or medication was started on or after the date of the first dose date, then the event will be considered treatment-emergent and the event will be attributed to that treatment; if it occurred before the first dose in the treatment period (e.g., at admission), it will be attributed to the treatment administered in the previous period.
7. For AEs with missing or incomplete start dates, if it can be determined based on the available start date components or the stop date to which treatment group(s) the AE should be assigned to then the AE will be assigned to the appropriate treatment group. If it cannot be determined, then the AE will be assigned to all treatment groups received.

For treatment-emergent AEs (TEAEs), time since dose will be expressed in days, hours and minutes. If either time is missing, time since dose will be expressed in days.

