11.3. ADVERSE EVENTS / ADVERSE DRUG REACTIONS

Analysis of safety assessments will be performed using the Dose Selection Safety Population. Assessment of safety will be based on the incidence of AEs, AEs resulting in discontinuation, and SAEs by treatment. AE summaries will be provided showing the number and percentage of subjects who experienced at least one TEAE. TEAEs will also be tabulated by maximum severity and by maximum relationship to study drug. These summaries will be presented by body system and PT (MedDRA, version 20.0 or higher). SAEs and AEs resulting in discontinuation will be summarized separately. All AEs will be listed by subject for the Dose Selection Randomized Population.

Any AE occurring after treatment start will be considered as a TEAE. Rules related to assigning TEAEs to treatment and imputation related to missing data are described in the Section 7.3.

Subjects may be counted under multiple system organ classes (SOCs) and PTs, but for each SOC and PT, subjects are only counted once.

The number and percentages of subjects with TEAEs as well as the number of events will be displayed. SOC's will be sorted by descending frequency of subjects. Within each SOC the PTs will be sorted by descending frequency of subjects.

Imputation related to missing AE data is described in the Section 7.3.

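### SAP 8.5 counts concomitant antiemetic use from Screening, so use that ended before dosing would be charged to the nalbuphine dose given later

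*SAP*

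**What the plan says.** SAP 8.5 defines two windows, both measured from Screening: "Prior medication is defined as medication taken up to 30 days before the first screening date", and "Non-study medication taken from the first Screening visit until the completion of the Follow-up visit will be considered as concomitant". Prior and concomitant medications are otherwise only listed. The one summary built on the second window is for antiemetics: "The incidence of concomitant antiemetic medication use will be tabulated by cohort", and by active drug or placebo. Neither SAP 8.5 nor the matching sentence in Protocol 8.1.8 limits that summary to use after dosing.

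The Screening anchor comes from Protocol 4.6.1, which describes what is to be collected as concomitant medication: "All medications taken by subjects after Screening until the completion of the Follow-up visit will be documented".

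Two other parts of the SAP use study treatment as the anchor. In SAP 7.3, "AEs and medications with incomplete start dates and times will be considered as treatment-emergent or prior/concomitant, respectively", following a numbered algorithm whose second step reads: "If a medication started and stopped prior to the start of study treatment the medication will be considered prior". For adverse events, SAP 11.3 says: "Any AE occurring after treatment start will be considered as a TEAE".

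**The concern.** A window that starts at Screening suits data collection, but it is a poor basis for attributing use to a dose. An antiemetic taken and finished before study drug cannot have been prompted by that drug. Under SAP 8.5 it would still enter the numerator for the cohort the subject later joined.

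Nausea and vomiting are among the Part A stopping criteria (Protocol 4.9.2), so a reader is likely to take antiemetic use by dose as a sign of tolerability. Adverse events are protected from this misattribution by the treatment-emergent rule; the antiemetic table is not. The treatment of a pre-dose record also depends on something irrelevant, namely whether its start date and time were fully entered.

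**Working it through.** There is no figure in the plan to reproduce, because the table is descriptive. The check compares the rules and then works out the weight of one record.

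1. **Distance between the two boundaries.** SAP Table 2 allows Screening from Day -30 to Day -2, so Screening precedes dosing by 2 to 30 days.

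2. **One record under each rule.** Take an antiemetic started and stopped on Day -1, with the stop date and time known.
   - Start date and time complete: the 7.3 algorithm is not engaged. SAP 8.5 alone applies, the record is concomitant, and the table counts it.
   - Start time missing: the 7.3 algorithm is engaged. Step 2 makes the record prior, and the table does not count it.
   - An adverse event on the same day: not treatment-emergent under SAP 11.3, so not counted.

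3. **Whether such a record can arise.** Protocol 4.6.1 bans non-prescription products "within 7 days prior to first drug administration and throughout the study"; the corresponding period for prescription products is 14 days. With Screening on Day -30, 30 - 7 = 23 days and 30 - 14 = 16 days fall outside those dated bans. With Screening on Day -7 or later, neither leaves any. The same section also carries an undated prohibition on concomitant medication, with exceptions for investigator-prescribed treatment of clinical events and case-by-case exemptions. That leaves prescribed use, exempted use and deviations. One route is visible in the Protocol. The naloxone challenge takes place on Day -1, and a subject continues with a Clinical Opiate Withdrawal Scale score below 5. Nausea scores 2 and vomiting 3 on that scale (Protocol 11.3), and Protocol 4.7 permits antiemetics for nausea and vomiting. Nothing in the documents shows that this happened.

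4. **Weight of one record.** Each cohort has 6 active and 2 placebo subjects (SAP 3.2). For a subject with no antiemetic after dosing, one pre-dose record adds 1/6 = 16.7 percentage points to the active cell or 1/2 = 50 points to that cohort's placebo cell. If the subject also took an antiemetic after dosing, it adds 0.

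5. **Direction.** SAP Table 2 places randomization on Day 1 before dosing, so use that ended earlier cannot depend on the assignment. The subject is active with probability 6/8 = 0.75 and placebo with probability 2/8 = 0.25. The expected addition is 0.75 × 16.7 = 12.5 points for active and 0.25 × 50 = 12.5 points for placebo, so the expected change in the active-minus-placebo difference is 0.

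**The case against.** The case for leaving the plan alone is substantial. SAP 8.5 follows the Protocol's own labelling of post-Screening medication. The Part A schedule leaves the concomitant-medication row blank at Screening and Day -1, although the adverse-event row is marked at both, so pre-dose records may never have been collected. SAP 7.3 step 6, for a missing start time, sends what happened before a period's first dose to the previous treatment, which suggests that nobody meant to charge it to the next one. The table belongs to the baseline and medication section rather than the safety section, and it supports no test. The listing is chronological with all collected data, so a stray record in a cohort of 8 would be easy to see. The table is also absent from the SAP Section 15 index and the mock-ups are not available, so a limit stated there cannot be ruled out.

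Most of this stands, and it bears on how often the problem arises and how much it matters. It does not change what SAP 8.5 says. Protocol 4.6.1 still requires documentation from Screening, and step 6 covers neither complete dates nor a single-dose part with no previous treatment.

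Three stronger readings are tempting and not supported:
- *That 8.5 and 7.3 conflict for every record, leaving the governing rule unstated.* The 7.3 algorithm is introduced for incomplete start dates and times. For a fully dated record, 8.5 governs alone.
- *That subjects could use antiemetics freely for up to 16 or 23 days before dosing.* Those counts consider only the dated bans and ignore the undated prohibition.
- *That the table is biased for or against nalbuphine, or misled dose escalation.* The expected shift in the difference is zero, and the stopping rules in Protocol 4.9.2 do not use antiemetic counts.

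**Conclusion.** The point holds as a minor flaw in an analysis rule. Followed literally, SAP 8.5 attributes finished pre-dose antiemetic use to a later dose, and the classification of such use depends on date completeness. The number of affected records is unknown, should be very small and may be zero. The 16.7- and 50-point figures show only how heavily one hypothetical record weighs in cells of 6 and 2; they do not estimate an error in the results. They assume that the record was collected, that the subject took no antiemetic after dosing, and that the placebo cell is a single cohort's. No hypothesis test or DRC escalation decision is affected.

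**What to change.** In SAP 8.5, restrict the antiemetic incidence table to use starting at or after study drug administration, selected with the time since dose that SAP 7.2 already defines for concomitant medications. Footnote any antiemetic started earlier and still ongoing at dosing. Keep all pre-dose use in Listing 16.2.4.4.

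Apply the dosing-based rule of 7.3 step 2 to complete and incomplete dates alike. SAP 7.3 calculates time since dose only when both dates are complete, so incompletely dated records still need the algorithm there to place them.

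The collection window in Protocol 4.6.1 can stay as it is. One line in SAP Section 5 should say that the analysis definition is narrower than the collection window. The table could be added to the Section 15 index at the same time. The cost is a few sentences and one programming filter; no new data are needed.

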9. PHARMACODYNAMICS ASSESSMENTS AND ANALYSIS

The abuse potential of nalbuphine will be assessed through evaluation and integrative interpretation of the pattern of results across the various types of measures: measures of positive response (i.e., measures most predictive of the drug's abuse potential and reinforcing properties), measures of negative response (i.e., measures that potentially mitigate against abuse potential), measures of stimulant effects, measures of other effects and measures of cognitive and psychomotor effects.

9.1. PHARMACODYNAMIC ASSESSMENTS

9.1.1. Pupillometry

Pupillometry will be used as an objective physiological PD measure as it is a sensitive measure of central opioid/stimulant action and appears to be resistant to tolerance development with repeated administration. An electronic pupillometer (NeuroOptics) will be used to measure pupil diameter. Data from a series of frames will be used in the calculation, and the final display will show the weighted average and SD of the pupil size. Measurements will be collected under mesopic lighting conditions. For each subject, every effort will be made to use the same eye for all assessments throughout the study.

Pupillometry will be recorded at the following time points:

- Pre-dose and at 0.25, 0.5, 1, 1.5, 2, 2.5, 3, 4, 5, 6, 8, 10, 12 and 24 hours post-dose.

PD pupillometry data in the Dose Selection Phase will be analyzed for the Dose Selection Safety Population. The exploratory endpoints are MPC, TMPC, and TA_PAOC.

9.1.2. Derived and Imputed Data

For each subject and treatment period, the parameters will be derived using the following rules:

- Analyses will be based on actual assessment times, except for pre-dose (baseline) times, which will automatically be considered as time 0 as appropriate for analysis. If the actual time is missing, the nominal time will be used.
- TMPC will be calculated as the time from time 0 to MPC.
- TA_PAOC is calculated as the area over the curve (AOC) divided by the time from time 0 (or the 0.25 hour time point if the VAS is not collected pre-dose) to the 24 hour time point. AOC is calculated using the linear trapezoidal rule applied to non-missing data.

- Missing data for subjects who are administered all scheduled study treatments for all the treatment periods will be considered as random non-informative missing for analysis purposes. Missing values will be examined on a case-by-case basis to confirm this. Reasons for missing data will be displayed in the listings. No further imputation will be applied to any missing values.

Assessments done outside the assessment windows may be excluded from by-time point summary statistics; this will be determined prior to unblinding.

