One (1) study (NAL 20) evaluated opiate withdrawal-related effects in subjects with osteoarthritis after administration of nalbuphine ER tablets for 21 days followed by abrupt study drug discontinuation. The objective opiate withdrawal scale (OOWS) scores obtained from the study showed an absence of any physical withdrawal symptoms in most active arm subjects scored (85% of subjects scored) or minimal evidence of physical withdrawal symptoms.

Nalbuphine was well absorbed following oral administration of nalbuphine ER tablets in healthy volunteers. The median time of observed peak concentrations ( $T_{max}$ ) was 3 to 6 hours after oral doses of up to 162 mg nalbuphine ER tablets, while the median  $T_{max}$  of nalbuphine was 0.5 hours after oral administration of 54 mg nalbuphine as a solution (Nubain®) (equivalent to 60 mg nalbuphine HCl solution). Exposure (area under the curve; AUC) of nalbuphine after single dose administration of Nalbuphine ER tablet and oral solution was shown to be comparable with a relative bioavailability of 94% under fasting conditions. However, as expected, the rate of absorption for the ER tablet is slower than the rate of the oral solution with a reduced maximum observed plasma drug concentration ( $C_{max}$ ) and delayed  $T_{max}$  (5.8 hours compared to 0.5 hours, respectively), which would be expected from the ER mechanism of this formulation.

Coadministration of nalbuphine ER tablets with a high caloric meal did not affect  $T_{max}$  but  $C_{max}$  values were approximately 1.5-fold higher compared to dosing under fasting conditions (Study NAL 06). However when administered as a nalbuphine solution, the food effect was less pronounced with an 11% decrease in  $C_{max}$  and approximately 24% increase in AUC under fed relative to fasting conditions.

The mean elimination half-life ( $t_{1/2}$ ) of nalbuphine varied between 6.6 and 9.6 hours across clinical studies. Nalbuphine is metabolized by the liver, possibly undergoes enterohepatic circulation, and is excreted via the kidneys. Nalbuphine metabolites are reported to be pharmacologically inactive.

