The median  $T_{max}$  of nalbuphine is expected to occur between 0.5 and 1.5 hours post-dose after oral administration of nalbuphine solution, while the median  $T_{max}$  is expected to occur between 3 and 6 hours post-dose after nalbuphine ER tablets. The PK sampling in the Treatment Phase was developed to capture the expected  $T_{max}$  of nalbuphine of both nalbuphine formulations. The mean  $T_{max}$  for orally-administered hydromorphone HCl solution is expected to occur at approximately 0.7 hours. In addition, the  $t_{1/2}$  of nalbuphine ranges from 6.6-9.6 hours, whereas the  $t_{1/2}$  for hydromorphone is approximately 2.3 hours. Based on this, a 24-hour assessment period and 24-hour post-dose discharge for each treatment visit is considered safe for the subjects, and at this time the PD measures are expected to return to approximately baseline. A minimum 4-day washout between each dose in the Treatment Phase is considered acceptable based on the  $t_{1/2}$  of the active agents to be used in this study, as it is a duration that is longer than five times the maximum  $t_{1/2}$  of the longest acting drug in the study, as recommended in the FDA guidance.

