TE _{min}	Response at time i (E _i) at times t _i over one inter-dosing Interval Time at time i (time_i)	$TE_{\min} = \min_j \{t_j \mid E_j < E_i \forall i\}$	The first time of trough response is used if the trough is obtained more than once
TA_AUE (AUE)	PD effect score E _i at actual elapsed times t _i over one inter-dosing interval.	$AUE_i = (t_i - t_{i-1}) \frac{(E_i + E_{i-1})}{2}$ 
Then:
 $AUE = \sum_{i=1}^n AUE_i$, summation over all time intervals until the last non-missing PD score.	Trapezoidal rule used to the 2 consecutive non-missing data points Missing data are ignored. The actual elapsed time t ₀ for the pre-dose value is set to 0.

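### If the 24 h pupil reading is missing, SAP 9.1.2 divides a 12 h area by 24 h, so that subject's TA_PAOC is understated whenever constriction lasts past 12 h

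*SAP*

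**What the plan says.** SAP 9.1.2 defines TA_PAOC as the area over the curve (AOC) divided by the time from time 0 "to the 24 hour time point. AOC is calculated using the linear trapezoidal rule applied to non-missing data". The divisor is tied to the 24 h time point. The area is tied to whatever readings exist.

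SAP 9.1.1 schedules pupillometry as "Pre-dose and at 0.25, 0.5, 1, 1.5, 2, 2.5, 3, 4, 5, 6, 8, 10, 12 and 24 hours post-dose". The last interval therefore runs from 12 to 24 h.

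Imputation is ruled out twice: SAP 7.3 states "Missing values for PD assessments will not be imputed" and SAP 9.1.2 states "No further imputation will be applied to any missing values". SAP 9.1.2 adds that missing values are reviewed case by case and that the reasons for them are listed.

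SAP Appendix A has no entry for TA_PAOC. Its entry for the analogous TA_AUE describes a "summation over all time intervals until the last non-missing PD score", which agrees with reading the AOC as stopping at the last available reading. No text shortens the divisor, extends the area, or makes TA_PAOC non-evaluable when the 24 h reading is absent.

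**The concern.** A time average needs the same window above and below the line. Followed as written, the rule gives a subject without a 24 h reading an area to 12 h over a divisor of 24 h. The result looks like a 24 h average but counts the second half of the day as no constriction. That subject stays in the dose-level summary, because pupillometry is analysed in everyone dosed (SAP 6.2 and 9.1.1).

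TA_PAOC is one of three pupil endpoints in Part A, and each cohort has only six subjects on nalbuphine, so one affected value can move a dose mean. The SAP is stricter with the comparable pharmacokinetic quantity: SAP 10.3 flags AUCinf when more than 20% of it is extrapolated and leaves it out of summaries. TA_PAOC has no equivalent check, although half its window can be empty.

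**Working it through.** The plan states no TA_PAOC value, bias or missing-data rate, so there is no figure to reproduce. The check applies the SAP's own trapezoidal rule to its own schedule.

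**Inputs from the documents**
- Reading times: 0, 0.25, 0.5, 1, 1.5, 2, 2.5, 3, 4, 5, 6, 8, 10, 12 and 24 h (SAP 9.1.1).
- Divisor: 24 h (SAP 9.1.2).
- Plasma half-life: Protocol 1.1 says that the mean value "of nalbuphine varied between 6.6 and 9.6 hours across clinical studies".
- Time of peak: Protocol 3.2.2 says that, for the solution, the median Tmax "of nalbuphine is expected to occur between 0.5 and 1.5 hours post-dose".
- Subjects on nalbuphine per cohort: 6 (Protocol 3.1.2).

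**Assumed.** The pupil profile is not given. I take a linear rise to a peak of 1 at 0.5 or 1.5 h, followed by the decline shown in the table. Using the plasma half-life and Tmax for the pupil effect is an assumption.

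**Share of the axis lost:** (24 - 12)/24 = 50%.

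**Formula.** With the 24 h reading, TA_PAOC = [AOC(0-12) + AOC(12-24)]/24. Without it, TA_PAOC = AOC(0-12)/24. Hence

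understatement = AOC(12-24) / [AOC(0-12) + AOC(12-24)].

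**Worked case: half-life 6.6 h, peak at 0.5 h.** The effect is 0.2989 at 12 h and 0.0848 at 24 h.
- AOC(12-24) = 12 × (0.2989 + 0.0848)/2 = 2.302.
- AOC(0-12) by trapezoids = 6.938.
- Complete record: 9.239/24 = 0.385. Without the 24 h reading: 6.938/24 = 0.289.
- Understatement = 2.302/9.239 = 24.9%.

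| Assumed decline after the peak | Understatement, peak at 0.5 to 1.5 h |
|---|---|
| Resolved by 12 h | 0% |
| Half-life 3 h | 9.4-10.7% |
| Half-life 4 h | 14.9-16.3% |
| Half-life 6.6 h | 24.9-26.4% |
| Half-life 9.6 h | 31.5-33.0% |
| Linear return to baseline at 24 h | 25.5-26.7% |
| Flat to 24 h | 50.5-51.6% |

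**Effect on a dose mean.** With one affected subject of six, and subjects otherwise alike: 24.9%/6 = 4.2% and 33.0%/6 = 5.5%.

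**Would dividing by the last available time repair it?** The ratio to the complete-record value is [AOC(0-12)/12] / [AOC(0-24)/24].
- Half-life 6.6 h, peak at 0.5 h: (6.938/12)/(9.239/24) = 1.50.
- Half-life 9.6 h, peak at 1.5 h: (8.118/12)/(12.111/24) = 1.34.
- Resolved by 12 h: 2.0.

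That change would exchange understatement for overstatement.

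**Interior gaps.** If the 12 h reading is missing but the 24 h reading is present, the trapezoid bridges the gap and the value shifts by only about 2% (half-life 8 h). The problem is specific to a missing end of the record.

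**The case against.** Several points on the other side are sound.

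- **The size is not known.** A reader might infer a loss of at least 25%, or treat 50% as typical. The documents support neither. Faster recovery takes the loss towards zero. The flat profile sits badly with Protocol 3.2.2, which says, in a passage written for Part B, that "at this time the PD measures are expected to return to approximately baseline" (24 h after dosing). That statement does not remove the problem, since a linear return to baseline at 24 h still gives about 26%. The half-life is also a weak proxy: no document ties miosis to plasma half-life, and Protocol 1.1 shows an earlier, higher peak for the solution than for the tablet.
- **The direction is not fixed.** A reader might infer that the error always favours less drug effect. It is zero once constriction has resolved. If the pupil were wider than baseline after 12 h and signed area were used, it would reverse. The SAP does not say how such area is treated.
- **The gap would be visible.** SAP 9.1.2 lists reasons for missing data, and a pupillometry listing is planned. What stands is that the derived TA_PAOC itself carries no flag and is not excluded.
- **The trigger should be uncommon.** Subjects stay in the unit until about 24 h and until final assessments are done (Protocol 3.1.2). No missing-data rate is given.
- **Little rests on it.** TA_PAOC is exploratory and descriptive, and Protocol 3.1.2 says that PD data do not drive escalation. A shift of 4-5.5% is small beside sampling error. If pupil variability resembled the 46-54% quoted for nalbuphine exposure in Protocol 12.2, which is only an analogy, the standard error of a mean of six would be 46/√6 = 19% to 54/√6 = 22%.
- **The Appendix A wording is for TA_AUE.** It is supporting evidence only.

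These points limit the size and the consequence. None supplies a rule that corrects the mismatch.

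**Conclusion.** The point holds as a minor defect. This is a stated rule that gives a wrong value in one identifiable situation, not merely missing detail. With the 24 h reading absent, TA_PAOC is understated whenever constriction persists past 12 h. The range runs from 0% to about half. It is roughly 25-33% if constriction peaks at 0.5-1.5 h and decays with a 6.6-9.6 h half-life, and one such subject in six then lowers the dose mean by about 4-5.5%.

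A reader might go further and conclude that the pupil results as a whole are biased. The documents do not support that. Maximum pupil constriction and its time are essentially unaffected unless the peak falls at the missing reading, and TA_PAOC is correct for every subject with a 24 h value.

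**What to change.** Add one sentence to SAP 9.1.2: TA_PAOC is derived only for subjects with a 24 h reading; otherwise it is set to missing, and the AOC to the last available reading is listed with a flag. Do not simply replace the divisor with the last available time, for the reason shown in the working.

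The cost is that a subject without a 24 h reading drops out of this one summary, even where constriction had already resolved by 12 h and the present rule would have been right. A common 0-12 h window for all subjects is an alternative, but it changes the endpoint for everyone.

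If no 24 h reading is missing, the sentence changes no result. Part A is complete (SAP 2.1 and 5), so this can be checked directly; the rule should be settled before TA_PAOC is tabulated. TA_PAOC is also a secondary endpoint in Part B (Protocol 2.2.3.1), where pupillometry again ends with readings at 12 and 24 h (Protocol Table 3), so the same sentence belongs in that plan.
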